6 GENERAL STATISTICAL CONSIDERATIONS

6.1 General Principles

All continuous variables will be summarized using the following descriptive statistics: n (non-missing sample size), mean, standard deviation, median, maximum and minimum. The frequency and percentages (based on the non-missing sample size) of observed levels will be reported for all categorical measures. In general, all data will be listed, sorted by site, treatment and subject, and when appropriate by visit number within subject. All summary tables will be structured with a column for each treatment in the order (Experimental, Control) and will be annotated with the total population size relevant to that table/treatment, including any missing observations.

Summary statistics for discrete data will include estimates and confidence intervals for binomial data; contingency tables, along with summary analyses such as tests of independence. Two-by-two tables may also include summaries of risk differences or risk ratios as is appropriate along with their confidence intervals.

Tabulations will be used extensively to summarize the data and will include summary statistics. For continuous data, tables will include measures of central tendency such as the mean, geometric mean, or median, and measures of dispersion such as the standard deviation or inter-quartile range. Tables of discrete data will include proportions and their confidence intervals.

Unless noted, statistical analyses will use standard methods as described below.

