6.3 Analysis Populations

The **Safety** population will include all enrolled subjects, summarized according to the actual vaccination received.

The **Per Protocol (PP)** analyses will include all subjects receiving two injections within window as assigned by the randomization schedule, and not experiencing any other major protocol deviations prior to their week 8 visit. Major protocol deviations include ineligibility, product administration deviations, and primary endpoint missing data. The subjects will be analyzed based on product actually received, regardless of randomization assignment. If subjects receive study vaccine for one visit and placebo for the other, then they will be included in the PP population until they receive the second injection or are otherwise removed from the PP population. The PP analyses will also include subjects determined to be CHIKV infected prior to the receipt of their scheduled second injection and not experiencing any other major protocol deviations prior to their state of infection. Subjects will be censored from the immunogenicity analysis following PCR-confirmed CHIKV infection. Immunogenicity and infection rates will both be examined for the PP population.

The **Intent-to-treat (ITT)** population will include all enrolled subjects, analyzed according to the randomized treatment. The ITT population will be used to analyze immunogenicity and infection rates.

The **Modified intent-to-treat (mITT)** analyses will include all enrolled subjects that received at least one product administration with non-missing immunogenicity data at their Week 8 visit, analyzed according to the study product(s) received. This definition will exclude subjects with protocol deviations related to possible dosing errors. The mITT population will only be used for immunogenicity analyses.

Subjects excluded from Immunogenicity (or CHIKV Incidence) analyses are listed in Appendix III, **Listing 16.2.3**.

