8.3 Adverse Events

The severity of an adverse event (AE) is defined as: Grade 1 (Mild), Grade 2 (Moderate), Grade 3 (Severe), Grade 4 (Life-threatening), and Grade 5 (Death). Only the single AE that is assessed as the primary cause of death should be assigned “Grade 5” severity.

Relation of an AE to the study product is defined as Definitely Related, Probably Related, Possibly Related, and Not Related. For purposes of preparing data reports in which AE attributions are limited to “Related” or “Not Related”, in this protocol, the “Definitely, Probably and Possibly” attributions will be mapped to the “Related” category.

AEs will be coded into MedDRA preferred terms.

When calculating the incidence of AEs (i.e., on a per subject basis), each subject will only be counted once and any repetitions of AEs within a subject will be ignored; the denominator will be the total population size. All AEs reported will be included in the summaries and analyses.

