8.3.1 Solicited Events and Symptoms

Solicited AEs will be recorded in the study database with data collection for 7 days after both the first and second study injections, without the collection of attribution assessments.

Following the study injection, the subject will remain in the clinic for observation for at least 15 minutes. After 15 minutes, blood pressure and pulse will be taken and the injection site will be inspected for evidence of local reaction before the subject leaves the clinic.

Subjects will be given a diary card to use as a memory aid, on which to record the solicited signs and symptoms daily for 7 days following each injection. The site may use a paper diary card as a source document or clinician notes obtained by telephone interview as the source for the information recorded in the study database. The solicited signs and symptoms on the diary card will include the following parameters: pain/tenderness at injection site, largest diameters of redness (erythema) and swelling (induration) at injection site, highest measured temperature per day, unusually tired/feeling unwell, muscle/body aches (other than at injection site), arthralgia (joint pain), headache, chills, and nausea.

At least one contact at about 7 days after each study injection will be conducted to complete the review of solicited diary card information. Subjects will be asked to contact the clinic at any time following each injection if they have any concerning signs or symptoms. Events that will require clinical evaluation include rash, urticaria, arthralgia, fever of 38.5°C (Grade 2) or higher lasting more than 24 hours, or significant impairment in the activities of daily living. Additionally, other clinical concerns may prompt a study visit based on the judgment of a study clinician.

The proportion of subjects reporting at least one solicited AE will be summarized by dose, treatment group and age stratum for each solicited adverse event, any systemic symptom, any local symptom, and any symptom. The 95% CI calculated using Clopper-Pearson methodology from a binomial distribution will be presented (**Table 14.3.1.1, Appendix I**).

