For each solicited systemic and local event, any systemic event, any local event, and any solicited event, the maximum severity over 7 days after each dose will be summarized for the safety population by treatment group and age stratum. The number and percentage of subjects reporting each event will be summarized by the maximum severity and treatment group, separately for each dose and over all doses. For each event the denominator is the number of subjects with non-missing data for the specific event (**Table 14.3.1.2, Appendix I**).

The number and proportion of subjects reporting a solicited AE will be summarized pre-dose and for each day post-dose for each injection and for all injections combined both in a summary table by treatment group and age stratum (**Table 14.3.1.3, Appendix I**) and graphically in a bar chart (**Figure 14.3.1.1, Appendix II**). A comparison of the event rate of solicited adverse events for each treatment group between dose 1 and dose 2 will be presented by age stratum (**Tables 14.3.1.4-14.3.1.5, Appendix I**).

Solicited AEs by subject will be presented in **Listing 16.2.7.1, Appendix III**.

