8.3.2 Unsolicited Adverse Events

All unsolicited AEs will be recorded in the study database from receipt of first study injection through 4 weeks after the last study injection administered. At subsequent follow-up visits, only SAEs and new chronic medical conditions will be recorded through the last study visit.

The proportion of subjects reporting at least one unsolicited AE will be summarized by MedDRA system organ class and preferred term for each injection, age stratum, and treatment group and over all injections. Denominators for percentages are the number of subjects who received the injection being summarized. A 95% CI will be presented along with a Fisher's exact test comparing the treatment groups and testing the difference in the proportion of subjects reporting an unsolicited AE for each MedDRA system organ class and preferred term (**Table 14.3.1.6, Appendix I**).

Unsolicited AEs by subject will be presented in **Listing 16.2.7.2, Appendix III**.

The following summaries for unsolicited AEs will be presented by MedDRA system organ class (SOC), preferred term, dose, age stratum, treatment group, and site:

- *Subject level summary of severity and relationship to study product (**Tables 14.3.1.7.1-14.3.1.7.2, Appendix I**);*
- *Subject incidence of AEs over time (Days 1-7, Days > 7) (**Tables 14.3.1.8.1-14.3.1.8.2, Appendix I**);*
- *Total frequency of AEs over time (Days 1-7, Days > 7) (**Table 14.3.1.9, Appendix I**);*
- *Subject listing of non-serious AEs of moderate or greater severity (**Table 14.3.2.2, Appendix I**);*
- *Bar chart of non-serious AEs by severity and MedDRA SOC (**Figure 14.3.1.2, Appendix II**);*
- *Bar chart of non-serious AEs by severity (**Figure 14.3.1.3, Appendix II**);*
- *Bar chart of non-serious AEs by relationship to study product and MedDRA SOC (**Figure 14.3.1.4, Appendix II**);*

- *Bar chart of non-serious AEs by relationship to study product (Figure 14.3.1.5, Appendix II).*

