		n	%	n	%										
Overall															
Any Local Symptom	None	x	x.x	x	x.x										
	Mild														
	Moderate														
	Severe														
	Not Reported														
[Local Symptom 1]	None														
	Mild														
	Moderate														
	Severe														
	Not Reported														
[Local Symptom 2]	None														
	Mild														
	Moderate														
	Severe														
[continue for all local symptoms]	Not Reported														
Site 1 [repeat for all sites]															
Any Local Symptom	None														

Severity is the maximum severity reported post dosing for each subject for each day.

TABLE 14.3.1.4:
Number and Percentage of Subjects Experiencing Solicited Events for Dose 1 Compared with Dose 2 by Treatment Group
Systemic Symptoms <<Overall/Site, Age Stratum>>

Treatment Group	Dose 1	Dose 2 – No Symptoms (N=X)	Dose 2 – Mild or Greater Symptom (N=X)	Dose 2 – Total (N=X)
CHIKV	No Symptoms (N=X)	x (x.xx)	x (x.xx)	x (x.xx)
	Mild or Greater Symptom (N=X)			
	Total (N=X)			
Placebo	No Symptoms (N=X)			
	Mild or Greater Symptom (N=X)			
	Total (N=X)			

Local Symptoms <<Overall/Site, Age Stratum>>

Treatment Group	Dose 1	Dose 2 – No Symptoms (N=X)	Dose 2 – Mild or Greater Symptom (N=X)	Dose 2 – Total (N=X)
CHIKV	No Symptoms (N=X)	x	x	x
	Mild or Greater Symptom (N=X)			
	Total (N=X)			
Placebo	No Symptoms (N=X)			
	Mild or Greater Symptom (N=X)			
	Total (N=X)			

TABLE 14.3.1.5:
Comparison of the Proportion of Subjects Experiencing Solicited Events by Treatment Group and Site <<Age Stratum>>

Symptom	Statistic	CHIKV Post Either Dose (N=X)	Placebo Post Either Dose (N=X)
Overall			
Any Symptom	Proportion	x.xx	x.xx
	95% CI (for proportion)	x.xx, x.xx	x.xx, x.xx
	Difference	x.xx	x.xx
	95% CI (for difference)	x.xx, x.xx	x.xx, x.xx
[Symptom 1]	Proportion		
	95% CI (for proportion)		
	Difference		
[continue for all symptoms]	95% CI (for difference)		
Site 1 [repeat for all sites]			
Any Symptom	Proportion		
	95% CI (for proportion)		
	Difference		
	95% CI (for difference)		

TABLE 14.3.1.6:
Number and Percentage of Subjects Experiencing Unsolicited Adverse Events with 95% Confidence Intervals by
MedDRA® System Organ Class, Preferred Term, Treatment Group and Dose Number <<Age Stratum>>
Post Dose 1 [Repeat for Dose 2 and Either Dose]

MedDRA® System Organ Class	MedDRA® Preferred Term	CHIKV (N=X)			Placebo (N=X)			Comparison of % subjects experiencing event (p-value) ¹
		n	%	95% CI	n	%	95% CI	
Overall								

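### SAP 8.3 sets a total-population denominator for AE incidence that conflicts with the non-missing rule in SAP 6.1 and 8.3.1, leaving the solicited-reaction rates in Tables 14.3.1.1 and 14.3.1.5 without a settled base

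*Combined protocol and SAP*

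**What the plan says.** Four statements in the SAP bear on the base for AE percentages.

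- **SAP 8.3**, the parent of the solicited and unsolicited sections, on per-subject incidence: "any repetitions of AEs within a subject will be ignored; the denominator will be the total population size". The safety population in SAP 6.3 "population will include all enrolled subjects, summarized according to the actual vaccination received", planned at 200 per arm.
- **SAP 6.1**, for the whole plan: "The frequency and percentages (based on the non-missing sample size) of observed levels will be reported for all categorical measures". It adds that summary tables are "annotated with the total population size relevant to that table/treatment, including any missing observations", so the N in a column header need not be the percentage base.
- **SAP 8.3.1**, for maximum severity of solicited events (Table 14.3.1.2): "For each event the denominator is the number of subjects with non-missing data for the specific event".
- **SAP 8.3.2**, for unsolicited AEs only: "Denominators for percentages are the number of subjects who received the injection being summarized".

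For Table 14.3.1.1, SAP 8.3.1 says only that "The proportion of subjects reporting at least one solicited AE will be summarized by dose, treatment group and age stratum", with Clopper-Pearson intervals. It names no denominator there, nor for Table 14.3.1.5. SAP 6.5 plans no imputation of missing values. The protocol's safety analysis section (6.4.2) gives no denominator for reactogenicity either.

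**The concern.** Table 14.3.1.1 reports the share of subjects with each solicited event. That is per-subject AE incidence, the quantity the 8.3 sentence addresses. A programmer who treats 8.3 as the rule for AEs would divide by the total population in Table 14.3.1.1 and by subjects with data in Table 14.3.1.2. The same symptom after the same dose would then carry two percentages in adjacent tables.

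The larger base also scores a subject with no second injection, or no diary, as free of symptoms. That is imputation in effect, although SAP 6.5 plans none. Nor need a missing second dose be random: SAP 4.4 lists related Grade 3 and Grade 4 AEs (self-limited Grade 3 reactogenicity excepted) and immediate hypersensitivity among the reasons for stopping injections, and SAP 5 does not replace subjects with incomplete injections. Local and systemic reactogenicity after each injection head the primary endpoints in SAP 3.2.1, so the base should not be left to a choice made at programming.

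**Working it through.** **1. Table by table.**

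| Table | Content | Denominator in the text |
|---|---|---|
| 14.3.1.1 | Rate and CI; post dose 1, post dose 2, either dose | None; 8.3 and 6.1 point different ways |
| 14.3.1.2 | Maximum severity, including a *None* row; same three column sets | Non-missing data for that event |
| 14.3.1.3 | By day, with a *Not Reported* row | None |
| 14.3.1.4 | Dose 1 by dose 2 cross-tabulation | None; no level for missing data |
| 14.3.1.5 | Between-arm difference; the shell has either-dose columns only | None; 8.3 and 6.1 point different ways |

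**2. The plan's own figures.** The documents give no figure for the denominator itself. The 10% loss in SAP 5 takes 200 to 200 × 0.90 = 180 per arm, the n of the safety power tables. SAP Table 2 reproduces at that n: 1 − 0.99^180 = 83.62% and 1 − 0.98^180 = 97.37%.

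**3. Size for a post-dose-2 rate.** Let p be the rate among subjects with data and d the share of the arm without data. The non-missing rule reports p; the total-population rule reports p × (1 − d). The 40% used for p is the phase 1 rate of mild systemic reactogenicity in protocol 1.3 (at least once after vaccination, n = 25), taken only as an example. The 10% is the plan's generic allowance, assumed here to apply to dose-2 diary data; 5% and 20% are further assumptions.

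| d | Subjects with symptom | Non-missing base | Total-population base |
|---|---|---|---|
| 5% | 76 | 76/190 = 40.0% (33.0 to 47.3) | 76/200 = 38.0% (31.2 to 45.1) |
| 10% | 72 | 72/180 = 40.0% (32.8 to 47.6) | 72/200 = 36.0% (29.4 to 43.1) |
| 20% | 64 | 64/160 = 40.0% (32.3 to 48.0) | 64/200 = 32.0% (25.6 to 38.9) |

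Intervals are 95% Clopper-Pearson. At d = 10% the rate falls by 4.0 points, a relative fall of one tenth.

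**4. Between-arm difference.** Take the 25% and 39.3% of SAP Table 3. If 10% of each arm had no data at all, 14.3 points would become 14.3 × 0.90 = 12.9, and exact Fisher power would go from 80.2% (180 per arm) to 78.5% (200 per arm at the diluted rates). That overstates the effect on Table 14.3.1.5. Every enrolled subject received dose 1, so a subject who misses dose 2 but returned a dose-1 diary still contributes to the either-dose columns. Only subjects with no solicited data after either dose are miscounted. If that were 2% of each arm (assumed), the difference would read 14.3 × 0.98 = 14.0 points.

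**5. Unequal missingness.** With equal true rates of 40% and an assumed 12% (vaccine) and 6% (placebo) without data, the total-population rule gives 0.40 × 0.88 = 35.2% and 0.40 × 0.94 = 37.6%, a false difference of −2.4 points. The documents give no source for any such split.

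**The case against.** The strongest reply is that the SAP, read as a whole, leans toward non-missing denominators. SAP 6.1 covers all categorical measures, and nothing says that 8.3 overrides it. SAP 6.5 argues against scoring a missing diary as symptom-free. The Table 14.3.1.1 shell has a separate N for each dose, which invites reading the dose-2 column as dose-2 recipients. Table 14.3.1.2 already gives every solicited event, any local, any systemic and any event on non-missing data, per dose and overall, so the undiluted rate (100% minus the *None* row) will be reported whatever is done in Table 14.3.1.1. Missing data are also partly visible, in the *Not Reported* rows of Table 14.3.1.3 and the dose counts of Table 14.1.3.

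Most of this stands, and it limits the point. It does not remove the conflict. SAP 6.1 lets the header N include missing observations, so the shells do not fix the percentage base, and SAP 8.3 states the opposite rule for AE incidence in plain terms.

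Two related criticisms fall away. The 8.3.2 rule concerns unsolicited AEs and does not conflict over solicited rates. Leaving subjects without data after both doses out of the paired Table 14.3.1.4 is ordinary practice and needs only a footnote.

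**Conclusion.** The denominator rules conflict as written, and one of them, if applied, biases post-dose-2 solicited rates downward. At an assumed 10% without dose-2 data, 40.0% reads as 36.0%; over 5% to 20% missing it reads as 38.0% to 32.0%. These sizes rest on the assumed share missing, since the SAP itself says there are no good data on loss to follow-up.

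A reader might infer that the plan as it stands dilutes the primary reactogenicity endpoint and its comparison with placebo. The documents do not support that. SAP 8.3 does not clearly prevail over 6.1, Table 14.3.1.2 carries the undiluted rates, and the difference in Table 14.3.1.5 is either-dose only, so a dose-2 loss does not carry over to it in full. A false between-arm difference would need unequal missingness that the documents neither state nor suggest.

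Severity is minor. SAP 5 and 6.8 set no formal hypothesis, so the effect is on descriptive rates and their intervals, and on agreement between tables.

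**What to change.** 1. In SAP 8.3, exclude solicited events from the total-population sentence.
2. In SAP 8.3.1, extend the Table 14.3.1.2 rule to Tables 14.3.1.1, 14.3.1.3 and 14.3.1.5: the denominator is subjects who received that injection and have non-missing solicited data for that event. For either-dose columns, require data after at least one dose.
3. Show the number without such data by arm in each of these tables. In Table 14.3.1.3 the *Not Reported* row can serve, given as a count.
4. Footnote Table 14.3.1.4 to say that it includes only subjects with solicited data after both doses.
5. State how a partly completed diary is handled. A subject with one symptom-free day and six missing days would otherwise still count as symptom-free, a milder form of the same bias.

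The cost is a few sentences of SAP text and some shell footnotes, with no new data or visits. It should be settled before the final tables are programmed.

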8.3.1 Solicited Events and Symptoms

Solicited AEs will be recorded in the study database with data collection for 7 days after both the first and second study injections, without the collection of attribution assessments.

Following the study injection, the subject will remain in the clinic for observation for at least 15 minutes. After 15 minutes, blood pressure and pulse will be taken and the injection site will be inspected for evidence of local reaction before the subject leaves the clinic.

Subjects will be given a diary card to use as a memory aid, on which to record the solicited signs and symptoms daily for 7 days following each injection. The site may use a paper diary card as a source document or clinician notes obtained by telephone interview as the source for the information recorded in the study database. The solicited signs and symptoms on the diary card will include the following parameters: pain/tenderness at injection site, largest diameters of redness (erythema) and swelling (induration) at injection site, highest measured temperature per day, unusually tired/feeling unwell, muscle/body aches (other than at injection site), arthralgia (joint pain), headache, chills, and nausea.

At least one contact at about 7 days after each study injection will be conducted to complete the review of solicited diary card information. Subjects will be asked to contact the clinic at any time following each injection if they have any concerning signs or symptoms. Events that will require clinical evaluation include rash, urticaria, arthralgia, fever of 38.5°C (Grade 2) or higher lasting more than 24 hours, or significant impairment in the activities of daily living. Additionally, other clinical concerns may prompt a study visit based on the judgment of a study clinician.

The proportion of subjects reporting at least one solicited AE will be summarized by dose, treatment group and age stratum for each solicited adverse event, any systemic symptom, any local symptom, and any symptom. The 95% CI calculated using Clopper-Pearson methodology from a binomial distribution will be presented (**Table 14.3.1.1, Appendix I**).

For each solicited systemic and local event, any systemic event, any local event, and any solicited event, the maximum severity over 7 days after each dose will be summarized for the safety population by treatment group and age stratum. The number and percentage of subjects reporting each event will be summarized by the maximum severity and treatment group, separately for each dose and over all doses. For each event the denominator is the number of subjects with non-missing data for the specific event (**Table 14.3.1.2, Appendix I**).

The number and proportion of subjects reporting a solicited AE will be summarized pre-dose and for each day post-dose for each injection and for all injections combined both in a summary table by treatment group and age stratum (**Table 14.3.1.3, Appendix I**) and graphically in a bar chart (**Figure 14.3.1.1, Appendix II**). A comparison of the event rate of solicited adverse events for each treatment group between dose 1 and dose 2 will be presented by age stratum (**Tables 14.3.1.4-14.3.1.5, Appendix I**).

Solicited AEs by subject will be presented in **Listing 16.2.7.1, Appendix III**.

